### 8.1 Premedication

#### 8.1.1 Premedication for Infusion-Related Reactions

##### 8.1.1.1 Infusion-Related Reactions

There is an inherent risk for IRRs with the administration of mAbs. An IRR is defined as an AE occurring during the IMP infusion and up to 24 hours after the EOI, which is assessed by the Investigator to be related to the infusion. Signs and symptoms of IRRs may include but are not limited to:

- facial flushing and swelling
- rash including urticaria
- headache
- fever
- chills, rigors
- diaphoresis
- tachycardia
- hypotension
- nausea
- dry mouth
- chest/back/abdominal pain/discomfort
- chest and throat tightness
- shortness of breath
- cough, wheeze, stridor
- hypoxia
- bronchospasm

- laryngeal edema
- angioedema
- shock

The risk of an IRR is highest for the first administration of a mAb and diminishes with subsequent infusions.

If an IRR occurs, it should be classified according to the CTCAE v5. Guidelines for grading and management of IRRs of all severities are provided ([Appendix 6](#)). In each case, the Investigator should use best clinical judgment in managing such reactions. *All  $\geq$  Grade 3 IRRs must be reported promptly to the Sponsor (or designee).*

#### 8.1.1.2 Premedication for Infusion-Related Reactions

Premedication for prophylaxis of IRRs will be mandatory prior to each dose of IMP.

The following agents are required; recommended doses are provided:

- Glucocorticoid therapy: equivalent to 80-100 mg IV methylprednisolone, approximately 0.5 to 2 hours prior to the start of Sym004 infusion
- Antihistamine (H1 antagonist): equivalent to 25-50 mg IV diphenhydramine, approximately 0.5 hours prior to the start of Sym004 infusion

The following agents are optional, and may be added to the premedication regimen at any time during the study at the Investigator's discretion; recommended doses are provided:

- Antihistamine (H2 antagonist): equivalent to 50 mg IV ranitidine or 30 mg IV famotidine or equivalent, approximately 0.5 hours prior to the start of Sym004 infusion
- Acetaminophen: 1000 mg IV (where available, or PO), or equivalent, approximately 0.5 hours prior to the start of Sym004 infusion

Note: Doses may be adjusted based on institutional practices. Administration of oral dexamethasone, 10 mg po, (or equivalent) 12 and 6 hours prior to administration of Sym004 is permissible in patients experiencing IRRs or if an increased incidence or severity of IRRs is observed.

#### 8.1.1.3 Premedication for Infusion-Related Reactions (Following an IRR)

For IRRs while in the study, the following premedication instructions are provided (for infusion prolongation instructions following an IRR, see [Section 8.2.1.1](#)):

- For Grade 1, Grade 2, or Grade 3 reactions, consider additional premedication or adjustment to premedications for subsequent infusions.
- For Grade 4 reactions, not applicable as no further treatment with IMP is allowed.

#### 8.1.2 Premedication for Dermatologic Toxicity

To minimize the risk of dermatologic toxicity, all patients will receive at minimum during Cycle 1 and 2 minocycline or doxycycline, and will apply topical therapy to the face and chest with a low potency steroid cream, and moisturizing creams/ointments to the hands and body. Use of

fragrance-free soaps will be encouraged throughout the treatment period. Guidelines for grading and management of dermatologic AEs of all severities are provided ([Appendix 7](#)).

### 8.1.3 Premedication for other IMP-Related Toxicities

Following the first dose, should a patient experience symptoms suggestive of other mild-to-moderate IMP-related reactions (e.g., nausea, vomiting, diarrhea, etc.), the patient may be premedicated with standard therapies to reduce the potential for such reactions in the future.

### 8.1.4 Institution of Mandatory Premedications

Based on ongoing review of patient safety data, the Sponsor may implement additional mandatory premedication for all patients treated in this study should a pattern emerge of other mild-to-moderate IMP-related reactions (e.g., IRRs and/or any other trends in IMP-related toxicities) that are amenable to prophylaxis with standard agents. Such action will occur following discussions between the Investigator(s) and the Sponsor's Medical Representative(s).

Any medications administered for either prophylaxis or therapy of signs/symptoms related to IMP will be documented on the appropriate page of the CRF.

## 8.2 Dose Modification Options

### 8.2.1 Prolongation of Infusion Duration

The option to prolong IMP infusion is most applicable during or following an IRR.

#### 8.2.1.1 Instructions for Infusion Prolongation

For IRRs, the following infusion prolongation instructions are provided (for premedication instructions, see [Section 8.1.1](#)).

- For Grade 1 reactions, the infusion may be slowed to 50% of the prior rate such that the remaining dose to be delivered is administered 2× longer than the amount of time that was initially scheduled.
- For Grade 2 reactions, the infusion should be interrupted for a minimum of 30 minutes, and at least until there is either amelioration to ≤ Grade 1 severity or return to baseline status. Supportive care should be provided. The infusion should then be restarted at 50% of the prior rate, as described above. Subsequent infusions should be administered at the prolonged rate.
- For Grade 3 reactions, the infusion will be STOPPED and supportive care will be provided. The patient will be either discontinued from treatment, or must receive subsequent treatments at a reduced dose and at a prolonged infusion rate (slowed to 50% of the prior rate or longer).
- For Grade 4 reactions, the infusion will be STOPPED and supportive care will be provided. The patient will be permanently discontinued from treatment.

In all cases, the Investigator should use best clinical judgment in managing such reactions.

All infusion interruptions and subsequent prolongations, including modified infusion times, as well as the toxicity that necessitated them, will be clearly documented on the appropriate page of the patient's CRF.

Note: Any assessments to be performed or samples to be collected (e.g., vital signs, PK) at the end of or following the EOI will still be performed or collected beginning at the delayed EOI timepoint

Guidelines for the grading and management of IRRs of all severities are provided ([Appendix 6](#)).

### **8.2.1.2 Treatment Following Infusion Prolongation**

To enhance patient safety following an infusion prolongation, subsequent infusions will be administered at the prolonged rate.

## **8.2.2 Dose Delay**

*All delays of IMP must be documented on the appropriate page of the patient's CRF.*

### **8.2.2.1 Delay Between Dosing**

AEs that warrant dose modification may be managed by delay in dosing, provided they do not meet the criteria for study discontinuation ([Section 9.1](#)).

In such cases, the period between any 2 scheduled doses may be extended as indicated to allow for amelioration of the toxicity. Such delays will be considered an extension within the current cycle.

### **8.2.2.2 Retreatment Following Dose Delay**

For AEs that are managed by dose delay, dosing may be restarted at the same dose, as clinically indicated. However, administration of IMP may only be restarted upon amelioration to  $\leq$  Grade 1, return to baseline status, or resolution of the observed toxicity, and provided all other retreatment criteria are met (see [Section 6.7.1](#)).

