
AE Management
	
Dose Delay AEs that do not meet the protocol discontinuation criteria, but nevertheless warrant dose modification, may be managed by temporary dose delay to allow for amelioration of the toxicity.
 
Dose Reduction In the event of Grade 3 treatment-related AEs that are self-limiting or can be managed by supportive care or other therapy, the patient may continue in the study if there is evidence of response, disease stabilization, or other clinical benefit, but must do so at a reduced dose of IMP. Patients may not be retreated until retreatment criteria are met. Once a patient has undergone dose reduction for any reason, the patient will continue to be treated at the reduced dose throughout the remainder of their time on study treatment.

Infusion-Related Reactions
	
Instructions for the grading and management of IRRs are provided. In all cases the Investigator should use best clinical judgment in managing such reactions.
 
 
• For Grade 3 reactions, the infusion will be STOPPED. The patient will be either discontinued from treatment or must receive subsequent treatments at a reduced dose and at a prolonged infusion rate.
 
• For Grade 4 reactions, the infusion will be STOPPED and the patient will be permanently discontinued from treatment.
 

Dermatologic Toxicity
	
Patients will be monitored weekly for evidence of dermatologic AEs.
 
Dose delay and/or inpatient dose-reduction(s) will be required upon occurrence of Grade 3 AEs, and may be implemented in the event of a Grade 2 dermatologic reaction that is debilitating for the patient.
 
Recommendations for management of Grade 1 to 3 dermatologic AEs are provided. Patients must be withdrawn from IMP treatment in the event of a Grade 4 dermatologic AE.

Hypomagnesemia, Hypocalcemia, and Hypokalemia
	
Patients will be monitored weekly for hypomagnesemia, hypocalcemia, and hypokalemia. In the event of Grade 3-4 hypomagnesemia, repletion is required as well as predosing electrocardiograms (ECGs) to monitor for QTc prolongation. For Grade 4 hypomagnesemia that is refractory to IV magnesium-replacement therapy, dosing with Sym004 should be delayed or reduced. Full management instructions are provided in the protocol.

SAFETY MONITORING
	

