## **8.2.3 Dose Reduction**

*All reductions of IMP dose must be documented on the appropriate page of the patient's CRF. Dose reduction may occur either during treatment cycles, or between cycles, as clinically indicated.*

In the event of Grade 3 treatment-related AEs that are self-limiting or manageable by supportive care or other therapy, the patient may continue in the study if there is evidence of OR, SD, or other clinical benefit, but must do so at a reduced dose of IMP. Patients may not be retreated until retreatment criteria are met (see [Section 6.7.1](#)).

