### 9.1 Criteria for Treatment Discontinuation

Patients will be discontinued from further treatment with IMP in the event of any of the following:

1. Progressive Disease: Confirmed radiographically (and evaluated according to RECIST v1.1)

*Note: Patients receiving futuximab or modotuximab with documented PD at the EOC2 (or prior to the EOC2) will be offered the opportunity to crossover to receive Sym004 or will be discontinued from study.*

2. Clinical Progression: Treatment failure not meeting the criteria for PD, but considered by the Investigator to require treatment discontinuation (i.e., global deterioration characterized by worsening PS, weight loss, and/or worsening clinical symptoms). **Every effort will be made to obtain imaging studies at the time of clinical progression.**

3. Adverse Event including:

- Hepatotoxicity characterized by:
  - AST and/or ALT elevation  $> 3 \times$  ULN (or  $> 3 \times$  baseline if elevated at study entry due to hepatic involvement by tumor), with
  - total bilirubin  $\geq 2 \times$  ULN without initial findings of cholestasis (i.e., serum ALP  $< 2 \times$  ULN), and
  - No explanation for the above findings such as viral hepatic injury, preexisting or acute liver disease, or another drug or condition capable of causing the observed injury

*Adapted from: Hy's Law. Drug-induced liver injury: premarketing clinical evaluation. Guidance for Industry. U.S. Department of HHS, FDA, CDER, CBER, 2009*

- Any of the following AEs:
  - Need for more than 2 dose reductions (Arm A), or more than 1 dose reduction (Arm B or Arm C)
  - Grade 4 IRR
  - Grade 4 EGFR-associated dermatologic AE
  - Torsade de pointes arrhythmia or other life-threatening arrhythmias
- Any other AE or SAE considered by the Investigator to require treatment discontinuation

Note: AEs resulting in a patient's permanent discontinuation from study treatment, regardless of seriousness or relationship to IMP, MUST be reported promptly to the Sponsor (or designee).

In the event of Grade 3 treatment-related AEs that are self-limiting or manageable by supportive care or other therapy, the patient may continue in study if there is evidence of response, disease stabilization, or other clinical benefit, but must do so at a reduced dose of IMP (see **Section 8.2.3**). Patients may not be retreated until retreatment criteria are met (see **Section 6.7.1**).

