### 12.2 Other Safety Surveillance Activities

At least one Medical Monitor will be assigned to review and evaluate relevant clinical/safety information concerning the clinical trial. The responsibilities of the Medical Monitor include, but are not limited to:

- Review of the site's assessment of eligibility
- Consultation with Investigator(s) regarding evaluation of patients to be enrolled to the study, treatment delays, restarts, and/or discontinuations
- Ongoing safety monitoring of all patients being treated in the study
- Evaluation of coding and trending of AEs in conjunction with the Drug Safety physician
- Performing surveillance on potential safety signals in conjunction with the Drug Safety physician
- Evaluating abnormal laboratory values and other relevant safety data, e.g., ECGs

- Providing medical support to the Sponsor in answering questions related to the study protocol
- Updating the Safety Team on trial status

A Drug Safety physician will be assigned to review, assess, and approve all SAE cases and associated reports. This physician will also perform the following:

- Assess for safety signals and trends in conjunction with the Medical Monitor
- Assist with questions regarding medical coding of SAEs
- Discuss with the Sponsor's Chief Medical Officer any cases which may present a concern regarding a signal or safety issue.

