**C. Dose Reduction Guidelines for IMP-Related Dermatologic AEs**

Dose delay and/or inpatient dose-reduction(s) will be required upon occurrence of Grade 3 anti-EGFR-associated dermatologic AE, and should be implemented according to the following tables (**Table 24**, **Table 25**):

Table 24: Dose Reduction for Grade 3 Dermatologic AEs - Sym004			
Dermatologic AE Grade 3	Immediate Action	Outcome Improvement	Sym004
First occurrence	Delay dose	Grade ≤1	Continue at same dose
		Grade 2	Reduce to 4.5 mg/kg
		No improvement	Discontinue
Second occurrence	Delay dose	Grade ≤1	Continue at same dose
		Grade 2	At dose of 6.0 mg/kg: Reduce to 4.5 mg/kg At dose of 4.5 mg/kg: Reduce to 3.0 mg
		No improvement	Discontinue
Third occurrence	Delay dose	Grade ≤1	Continue at same dose
		Grade 2	At dose of 6.0 mg/kg: Reduce to 4.5 mg/kg At dose of 4.5 mg/kg: Reduce to 3.0 mg/kg At dose of 3.0 mg/kg: Discontinue
		No improvement	Discontinue
Fourth occurrence	Discontinue	Any	Discontinue

Abbreviations (in alphabetical order): kg, kilogram; mg, milligram

Note: Dose reductions for 9 mg/kg loading NA. For dose delays, re-assess after ≤ 2 weeks. Longer delays are allowed if no recovery to < Grade 2 after 2 weeks

Table 25: Dose Reduction for Grade 3 Dermatologic AEs - Futuximab or Modotuximab			
Dermatologic AE Grade 3	Immediate Action	Outcome Improvement	Futuximab or Modotuximab
First occurrence	Delay dose	Grade ≤1	Continue at same dose
		Grade 2	Reduce to 1.5 mg/kg
		No improvement	Discontinue
Second occurrence	Delay dose	Grade ≤1	Continue at same dose
		Grade 2	At dose of 3.0 mg/kg: Reduce to 1.5 mg/kg At dose of 1.5 mg/kg: Discontinue
		No improvement	Discontinue

Abbreviations (in alphabetical order): kg, kilogram; mg, milligram

Note: Dose reductions for 9 mg/kg loading NA. For dose delays, re-assess after ≤ 2 weeks. Longer delays are allowed if no recovery to < Grade 2 after 2 weeks

In each case, the next treatment should be delayed, and the patient’s condition should be re-assessed after 1-2 weeks. Treatment should be delayed further if the AE remains at Grade 3 after 2 weeks.

In the case of a Grade 2 dermatologic AE which is locally debilitating for the patient, the guidelines outlined above may be followed at the Investigator’s discretion.

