### B. Management of Hypomagnesemia

Patients receiving IMP will be monitored weekly for evidence of hypomagnesemia, which should be managed as follows (Table 27):

Table 27: Management of Hypomagnesemia and QTc Prolongation	
Grade	Action
Grade 1-2	No replacement therapy required, weekly monitoring to continue, but may be administered at treating physician's discretion, weekly monitoring to continue
Grade 2 or higher	Use of concomitant QTc-prolonging drugs* should be discontinued unless urgently needed for medical care and no alternative therapy is available
Grade 3-4	Administer MgSO 4 (6 to 10g IV) at minimum 2 times per week until ≤ Grade 1 Perform predosing ECG (required) to monitor for QTc prolongation**  In the event of Grade 3 QTc prolongation potentially due to hypomagnesemia, Sym004 administration should be delayed while magnesium repletion is undertaken  Sym004 may be restarted with continued intensive magnesium therapy at the same dose or at a reduced dose once hypomagnesemia returns to ≤ Grade 1 severity, and once the QTc returns to WNL or baseline status  In the event of Torsade de pointes (TdP) or other life-threatening arrhythmias discontinue Sym004
Grade 4	For Grade 4 hypomagnesemia that is refractory to IV magnesium-replacement therapy, dosing with IMP should be delayed or reduced .

Abbreviations (in alphabetical order): g, gram; IV, intravenous

\* Listings of QTc prolonging drugs may be found at: <<https://crediblemeds.org/index.php?cID=222>>

\*\* ECG is required before IMP administration to monitor QT prolongation that may result in severe arrhythmias such as TdP.

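### For related AEs with no rule of their own, Grade 3 forces a reduced dose and evidence of benefit, but Grade 4 may be followed by a restart at full dose

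*Protocol*

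**What the plan says.** The protocol handles treatment-related toxicity through a general rule plus several event-specific ones.

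- **Delay.** Section 8.2.2.1: "AEs that warrant dose modification may be managed by delay in dosing, provided they do not meet the criteria for study discontinuation". No upper grade is given.
- **Restart after delay.** Section 8.2.2.2: "For AEs that are managed by dose delay, dosing may be restarted at the same dose, as clinically indicated". The conditions are recovery to Grade 1 or below, to baseline or to resolution, and the retreatment criteria of Section 6.7.1. There is no grade limit and no reference to Section 8.2.3.
- **Reduction.** Section 8.2.3 opens "In the event of Grade 3 treatment-related AEs that are self-limiting or manageable by supportive care or other therapy" and then allows continuation only with evidence of response, stable disease or other clinical benefit, and only at a lower dose. Section 9.1 repeats this, and so does the synopsis ("In the event of Grade 3 treatment-related AEs that are self-limiting or can be managed by supportive care or other therapy"). All three name Grade 3 only.
- **Discontinuation.** Section 9.1 names two Grade 4 events that end treatment: infusion-related reaction and EGFR-associated dermatologic AE. It lists Hy's Law-type hepatotoxicity, life-threatening arrhythmia and exceeding the permitted number of reductions separately. The rest is covered by "Any other AE or SAE considered by the Investigator to require treatment discontinuation".
- **Event-specific tables.** Tables 24 and 25 allow "Continue at same dose" after a Grade 3 dermatologic AE that recovers to Grade 1 or below. Table 27 covers Grade 3-4 hypomagnesemia with QTc prolongation: "Sym004 may be restarted with continued intensive magnesium therapy at the same dose or at a reduced dose". It also has a delay-or-reduce rule for refractory Grade 4 hypomagnesemia.

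Amendment 5 leaves the IMP doses unchanged (Section 6.5.4) and lets the two treated patients stay on Sym004 until progression (Section 6.7.3), so these rules are still in force.

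**The concern.** For related AEs without their own rule, such as diarrhea, stomatitis, hypocalcemia or hypokalemia, the general text is stricter at Grade 3 than at Grade 4. A patient recovering from Grade 3 related diarrhea must show benefit and take a lower dose. A patient recovering from Grade 4 related diarrhea, if not discontinued, may go back to the full dose with neither condition. The more dangerous event therefore gets the looser dosing rule. Safety is the only remaining purpose of the trial after Amendment 5.

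Section 8.2.2.2 has a second, related fault. It makes no exception for Section 8.2.3, so read alone it also allows a same-dose restart after a delayed Grade 3 AE, which Section 8.2.3 forbids.

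**Working it through.** The protocol states no figure to reproduce here. The check is a trace of the rules, followed by simple arithmetic for size.

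**Rule trace for a related AE with no rule of its own (example: diarrhea)**

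| Step | Grade 3 | Grade 4, Investigator does not discontinue |
|---|---|---|
| 9.1 stop | Not met | Not met: not one of the named Grade 4 stops |
| 8.2.3 | Applies | Does not apply: wording limited to Grade 3 |
| 8.2.2.1 delay | Permitted | Permitted |
| Recovery (8.2.2.2, 6.7.1) | Required | Required |
| Evidence of benefit | Required | Not required |
| Restart dose | Must be reduced | Same dose permitted by 8.2.2.2 |

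Section 6.7.1 adds neutrophil and platelet thresholds and recovery conditions, but no dose or benefit condition. The sentence in Section 11.5 on stopping IMP for severe reactions stands under overdose and does not apply here.

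**Dose difference (Table 6).** The first Sym004 reduction is from 6 to 4.5 mg/kg: 1 − 4.5/6 = 25%. Section 8.2.4 bars re-escalation, so the Grade 3 patient stays at the lower dose.

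**Frequency (Table 1, Section 2.4.1).** No Grade 4 rate is given. The Grade 3-or-higher figures give an upper bound for reactions without their own rule: asthenia 5.7%, anemia 4.6%, fatigue 3.5%, hypocalcemia 2.4%, diarrhea 2.2%, abdominal pain 2.2%, hypokalemia 1.9%, stomatitis 0.8%. The caption can be read as giving a share of the reactions rather than of the patients. For diarrhea that would be 0.254 × 0.022 = 0.56% of patients.

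**Chance that at least one of the two patients has related diarrhea of Grade 3 or higher**, assuming each carries the Table 1 risk independently:

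- at 2.2%: 1 − (1 − 0.022)² = 4.4%
- at 0.56%: 1 − (1 − 0.0056)² = 1.1%

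The chance of Grade 4 is lower by an amount the protocol does not allow us to compute.

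**The case against.** The best counter-reading is that Grade 4 is an implied stop. The Grade 3 sentence is a conditional permission, limited to self-limiting or manageable events and placed in Section 9.1 just after the list of stopping AEs, so worse events could be taken to have no permission to continue. Table 27 would then be a specific exception. This reading is possible, but it is not written anywhere. It also makes the two named Grade 4 stops in Section 9.1 redundant, and it sits badly with the clause leaving other AEs to the Investigator. If the sponsor did mean a stop, the text still needs to say so.

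It is also fair to say that Section 8.2.2.2 permits and does not instruct. A full-dose restart needs the Investigator to decide against stopping, against reducing, and in favor of the same dose. Other controls exist:

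- recovery before restart;
- 24-hour reporting of SAEs, which takes in most non-laboratory Grade 4 events (Sections 10.2.1 and 10.3.1);
- correction of significant electrolyte abnormalities before dosing (Section 7.2.7.2);
- dosing delay at a QTc of 500 msec or more (Section 7.2.8);
- a Medical Monitor role that includes "Consultation with Investigator(s) regarding evaluation of patients to be enrolled to the study, treatment delays, restarts, and/or discontinuations".

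All of these reduce the risk, but none sets the restart dose. A Grade 4 laboratory abnormality may not be reported as an SAE at all.

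Two further points stand in part. Same-dose restart after recovery is accepted for dermatologic AEs, so a strict ladder is not universal in this protocol; that is an event-specific choice, though, and does not explain why the general rule is reversed between grades. The frequency bound is loose: it includes the Grade 3 events already covered, and it draws on studies with Sym004 doses up to 12 mg/kg weekly and 18 mg/kg every second week.

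**Conclusion.** The concern holds. For treatment-related AEs outside the event-specific rules, the protocol requires a reduced dose and evidence of benefit after Grade 3, yet permits a same-dose restart without evidence of benefit after Grade 4 whenever the Investigator does not discontinue. The difference is 4.5 versus 6 mg/kg of Sym004.

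The practical reach is small. Accrual is halted and two patients are on treatment. For diarrhea, the chance that either is affected at Grade 3 or higher is at most 1.1% to 4.4%, depending on how Table 1 is read, and assuming independence and that Table 1 rates apply to these patients. The conclusion rests on the literal wording of Sections 8.2.2.1, 8.2.2.2, 8.2.3 and 9.1. It does not claim that Investigators would usually resume full dose, only that the text allows it. This should be corrected because it is a stated dosing rule that is less protective for the worse event.

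**What to change.** 1. In Section 8.2.3, Section 9.1 and the synopsis, extend the general rule from Grade 3 to *Grade 3 or Grade 4 treatment-related AEs that do not meet a Section 9.1 discontinuation criterion*. The Investigator's right to discontinue under Section 9.1 is untouched.
2. In Section 8.2.2.2, qualify the same-dose permission with *except where Section 8.2.3 requires a reduced dose*. This also removes the conflict with Section 8.2.3 at Grade 3.
3. In Section 8.2.3, state that Tables 24-25 (dermatologic AEs) and Table 27 (hypomagnesemia) apply instead for those events.

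If the sponsor intended other related Grade 4 AEs to end treatment, Section 9.1 should list that as a discontinuation criterion; the edit to Section 8.2.2.2 is needed either way.

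The cost is short wording changes in four places, with no effect on visits, data or analysis, though Section 13.4.1 means they must go through a formal amendment. The downside is slightly less Investigator discretion in rare Grade 4 events, including Grade 4 laboratory AEs, where a reduction would become mandatory.
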